Platelet-rich plasma (PRP) is an autologous solution of human plasma with a high concentration of platelets. Platelet-rich plasma contains various growth factors that enhance the healing process and regeneration by initiating the stages of cell proliferation, differentiation, angiogenesis, and chemotaxis. The rationale for use and therapeutic potential of a high concentration of platelets is based on their capacity to supply supraphysiologic amounts of essential growth factors and cytokines which then provide a regenerative stimulus, promoting tissue repair [8]. Important growth factors released from platelets during the healing process include platelet-derived growth factor (PDGF), transforming growth factor (TGF- β), vascular endothelial growth factor (VEGF), epidermal growth factor (EGF), basic fibroblast growth factor (bFGF), and insulin-like growth factor (IGF-1) [9].

PRP has been described for the treatment of various health conditions, from hair loss to joint injuries. PRP is most studied and used for the treatment of musculoskeletal soft tissue injuries, including tendinopathies and tendon tears, and ligament, muscle, and cartilage injuries [10]. The injection of PRP is not a new technology, but it has not been well-studied in the field of urogynecology. Two small series have reported on use of PRP

for the treatment of female SUI, suggesting successful treatment outcomes in up to 80% of patients [11] [12]. With this study, we will provide higher quality evidence on the use of PRP in the treatment of SUI.

This study will aim to determine the 6-month post-treatment efficacy of PRP injection in the treatment of **SUI.** Knowledge gained from this study has the power to change clinical practice by equipping physicians with a minimally invasive and likely low risk SUI treatment.

Approach

The primary aims of this study are to determine the efficacy and safety of PRP injection into the anterior vaginal wall for the treatment of SUI.

The primary efficacy aim will be determined by the following outcome measures:

- 1. Negative urinary stress test (no leakage noted on examination during cough or Valsalva maneuvers at a standardized bladder volume of 300 mL [13]
- 2. Subjective outcome with improvement in the Patient Global Impression of Improvement (PGI-I), with positive response defined as "very much better" (1) or "much better" (2). [14]

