Treatment "success" will be defined as a negative CST and a reported PGI-I of "very much better" or "much better" 6 months after treatment.

The primary safety aim will be assessed by monitoring adverse events classified by the Clavien-Dindo Classification.

Secondary Outcomes that will be compared between groups include:

- 1. Female Sexual Function Index (FSFI) scores
- 2. Incontinence-Quality of Life (I-QOL) scores
- 3. Perception of Monetary Value
- 4. Questionnaire for Urinary Incontinence Diagnosis (QUID)
- 5. Visual Analog Scale (VAS) for patient pain/discomfort
- 6. Visual Analog Scale (VAS) for procedure difficulty (by provider)

Eligibility Criteria

- 1. Women aged 18 years or older
- 2. Pure or stress-predominant urinary incontinence with the Medical, Epidemiologic, and Social Aspects of Aging questionnaire (MESA) stress incontinence symptom score greater than MESA urge incontinence symptom score
- 3. Observation of leakage by provocative stress test at bladder volume \leq 300 mL [15]
- 4. Post void residual < 150 mL

Exclusion criteria

- 1. Currently pregnant or trying to conceive
- 2. Currently breastfeeding
- 3. Interstitial cystitis

- 4. Urgency urinary incontinence predominance or currently being treated for overactive bladder with medication, percutaneous tibial nerve stimulation, bladder chemodenervation, or sacral neuromodulation
- 5. Currently being treated for a sexually transmitted disease
- 6. Pelvic organ prolapse greater than stage 2 according to the Pelvic Organ Prolapse Quantification System
- 7. Periurethral mass
- 8. Active gynecologic, urologic or colorectal cancer
- 9. Any history of cancer within the last 5 years
- 10. Mental disorder making the patient unable to provide consent
- 11. Undiagnosed abnormal uterine bleeding
- 12. Genitourinary fistula
- 13. Prior SUI surgery
- 14. Use of anti-platelet or anti-coagulant medication
- 15. Use of non-steroidal anti-inflammatories
- 16. Regular use of non-steroidal anti-inflammatories

Methodology

This is a single-blind prospective randomized controlled trial comparing the efficacy of injection of 5 mL PRP into the anterior vaginal wall versus injection of 5 mL injectable saline for the treatment of SUI in females.

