At baseline and at time points of 1 month, 3 months, and 6 months, subjects will complete the previously described validated questionnaires (see visit details below). At a 1-month telephone visit, a subset of the questionnaires will be administered, and patients will be queried about any adverse events. At baseline and at time points of 3 and 6 months, all validated questionnaires will be completed, as well as a pelvic exam with a urinary stress test, performed by a nurse practitioner specifically trained in urogynecology, and who did not perform the injections and thus blinded to the randomization. All adverse events will be recorded and classified per the Clavien-Dindo Classification.

Figure 1. Location and Depth of Injections¹²

At the end of the 6 months, subjects will be unblinded.

If subjects have symptoms of SUI which are refractory to treatment with PRP they will be referred to Urology or Urogynecology and will be offered standard of care following completion of the final study visit. If patients wish to receive alternative treatment for SUI prior to completion of 6-month follow-up they will be exited from the trial and final outcomes will be assessed at that time

Subjects will be provided a \$50 eVoucher upon completion of the 6-month follow-up visit.

Data will be stored in a secure REDCap database, only accessible to the research team members. Randomization envelopes and the Randomization Log will be kept in a locked cabinet.

Power Analysis

Sample size calculations were performed based on a desired power of at least 90% and assuming true response rates of 70% and 20% for treatment and placebo groups, respectively. The 70% response rate in the active PRP treatment group was chosen based on prior studies of PRP, as well as urethral bulking procedures [12] [16] [17]. The response rate of 20% in the placebo arm was chosen based on prior urethral bulking studies showing a 20% rate of negative CST after placebo [18]. Using an unadjusted alpha of 0.05, a sample of 38 subjects (19 per treatment group) is the minimum number required to have >90% power to detect a difference between the response rates of the two treatments.

In order to account for a 20% drop-out rate, we will plan to enroll a total of 50 patients (25 per treatment group).

Statistical Analysis and Data Reporting

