- Questionnaire for Urinary Incontinence Diagnosis
- Patient Global Impression of Improvement

3-Month Visit

Record any adverse events Pelvic exam with cough stress test Surveys

- Female Sexual Function Index
- Incontinence Quality of Life
- Questionnaire for Urinary Incontinence Diagnosis
- Patient Global Impression of Improvement

6-Month Visit

Record any adverse events Pelvic exam with cough stress test Surveys

- Female Sexual Function Index
- Incontinence Quality of Life
- Questionnaire for Urinary Incontinence Diagnosis
- Patient Global Impression of Improvement
- Perception of Monetary Value

\$50 eVoucher for completion of 6-month follow-up visit

Benchmarks for Success

After enrollment of the first 5 subjects, a quality control of the data collected and entry will be performed. Additional quality control will be performed by the PI after every 10 patients. Meticulous recording of adverse events will be performed. If adverse events are frequent and distressing, the project will be halted and data collected to that point will be analyzed.

After enrollment of 25 subjects, preliminary data and adverse events will be analyzed by a Data and Safety Monitoring Board made up of the research team members.

Potential Problems

Potential problems include low or slow enrollment. In addition to screening patients in the clinic, we can also plan on advertising the study via the University of Iowa listserv and/or advertisement materials to other clinics, such a family medicine, internal medicine, and gynecology.

Since this is a new procedure not well-described in the literature, another potential problem may be the learning curve of the procedure. To mitigate this, only two clinicians will serve as the injector, including the PI

and one other fellowship-trained FPMRS specialist. This will allow consistent and standardized procedure methods.

Timetable and Plan For Completing Project

February 2022: set up REDCap database

March 2022: complete IRB application (as of grant submission, the IRB application has been approved pending minor modifications)

June 2022: start screening clinics for eligible patients, enroll subjects

June 2022 - September 2023: enroll patients, collect data

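### The only written halting rule needs adverse events to be both frequent and distressing and ignores the recorded Clavien-Dindo grades, so one grave injection-related event does not trigger it

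*Combined protocol and SAP*

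**What the plan says.** The halting rule stands under Benchmarks for Success in the combined protocol and SAP: "If adverse events are frequent and distressing, the project will be halted and data collected to that point will be analyzed". It gives no count, rate, severity grade or test of relatedness.

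Severity is nevertheless recorded. Under Approach: "The primary safety aim will be assessed by monitoring adverse events classified by the Clavien-Dindo Classification". In the follow-up text under Injection Procedure: "All adverse events will be recorded and classified per the Clavien-Dindo Classification". No grade is linked to a halt, a pause or an expedited review.

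Benchmarks for Success has two further provisions. After an initial check of data and data entry at 5 subjects, "Additional quality control will be performed by the PI after every 10 patients". Once 25 subjects are enrolled, "preliminary data and adverse events will be analyzed by a Data and Safety Monitoring Board made up of the research team members". Breaking the Blind lets the investigator unblind one subject in a medical emergency.

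On what is known of the risk, Potential Problems says: "Since this is a new procedure not well-described in the literature". Significance and Innovation speaks of "equipping physicians with a minimally invasive and likely low risk SUI treatment".

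**The concern.** A rule that joins two conditions with *and* fails when either is absent. A single grave event may well be distressing, but one event is hardly frequent, so the sentence does not require a halt. Severity, which would normally drive such a decision, is collected and then not used in the only rule that could act on it.

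The stake is the protection of women not yet injected. Only two small series of PRP for this condition are cited, so the document offers little experience to fall back on. With 25 women per arm, an uncommon grave harm that appears at all will most likely appear first as a single case. Whether injections then continue rests on the judgement of the team that is running the trial.

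**Working it through.** The halting rule contains no number, so there is no stated figure to reproduce. The check has two parts.

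**1. Does any other text supply the missing pause?**

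| Provision | What sets it off | Does it pause injections after one grave event? |
|---|---|---|
| Halting rule (Benchmarks for Success) | Events both frequent and distressing | No: a single event is not frequent |
| Check at 5 subjects, then every 10 (same section) | Enrolment count | No: data quality control |
| Board review (same section) | Enrolment of 25 subjects | No: not event-triggered, and no criterion is stated |
| Emergency unblinding (Breaking the Blind) | One subject's medical need | No: concerns that subject's care only |
| Clavien-Dindo grading (Approach; Injection Procedure) | Every event | No: grades are recorded, no action is attached |

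No other part of the document mentions a halt or pause.

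**2. How likely is a lone event, and how often would a single-event rule act?**

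Inputs:
- 25 women per group and 50 in all, from Power Analysis ("In order to account for a 20% drop-out rate, we will plan to enroll a total of 50 patients").
- The per-woman risk *p* of a related grade III or higher event is not in the documents. I assume 0.1%, 1% and 5% to show a range.
- Events are taken as independent between women and fully ascertained. Loss to follow-up before an event is seen would lower the figures.

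Chance of at least one event among *n* women: P(X ≥ 1) = 1 − (1 − p)^n.

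| Assumed risk | Only the 25 PRP women at risk | All 50 women at risk |
|---|---|---|
| 0.1% | 1 − 0.999^25 = 0.025 (2.5%) | 1 − 0.999^50 = 0.049 (4.9%) |
| 1% | 1 − 0.99^25 = 0.222 (22%) | 1 − 0.99^50 = 0.39499 (39%) |
| 5% | 1 − 0.95^25 = 0.723 (72%) | 1 − 0.95^50 = 0.923 (92%) |

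The right-hand column applies if the risk comes from the blood draw or the injection itself, which both arms undergo.

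Chance that exactly one event is seen among the 25 PRP women, given at least one: P(X = 1) / P(X ≥ 1), with P(X = 1) = 25 × p × (1 − p)^24.
- At 1%: 0.196 / 0.222 = 0.884, or 88%.
- At 5%: 0.365 / 0.723 = 0.505, or 51%.

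So if a grave event occurs at a risk of 1%, it is nearly always alone. At 5% it is alone about half the time. The condition matters: at 1% the commonest result is no event at all, 1 − 0.222 = 0.778, or 78%.

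**The case against.** The rule says when the project must stop, not that it may stop only then. It can operate at any time, and nothing prevents the investigators from pausing after one bad event. This is a single-site study of about 50 women with two injectors, under IRB approval. The IRB application, where reporting duties and pause conditions could sit, is not among the documents. It may be over-strict to read an informal sentence as a logical test. All the rates above are assumed and span a fifty-fold range, so they show what is possible and not what is expected. Grade III is a reviewer's choice, the document does not define the grades, and the board to which a pause would go is the research team itself.

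Much of this stands. It limits the point to what this document obliges, and it makes the grade a proposal. It also means that the IRB, and not the board, brings independence to the review. It does not remove the gap: discretion is not a written commitment, and no text here commits the trial to pause after a single grave event.

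A reader might infer that the trial has no protection against a grave event, or would carry on regardless. The documents do not support that, since discretionary stopping is open and IRB rules are simply not shown. A reader might also infer that a halt ends safety follow-up for women already injected, because the rule refers to analysing the data in hand. The text is only silent on this: Methodology sets 6 months of follow-up after injection and Injection Procedure schedules the 1-, 3- and 6-month contacts, with no exception for a halt.

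**Conclusion.** The point holds as a gap in the written plan. Followed literally, the one halting rule is not met by a single grave injection-related event, and no other provision in this document fills that place. This is more than missing detail, because the severity data needed for a better rule are already collected. It does not threaten the validity of the trial, and it is best treated as a cheap improvement in participant safety.

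The documents cannot give the size of the problem. The figures in the working rest on assumed risks and serve to show two things: that a lone event is a realistic way for harm to appear, and how often a single-event rule might act.

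Two further steps are tempting and unsupported. One is to say that pauses would be uncommon. The protocol's expectation of low risk carries no number, and at a risk of 5% a pause is more likely than not. The other is to define frequency by a fixed count of lower-grade events. The documents give no rate from which to choose one, so any number would be an arbitrary trade-off between vigilance and needless interruption.

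**What to change.** Keep the existing sentence and add a second trigger, joined by *or*. Suggested wording: any single adverse event of Clavien-Dindo grade III or higher, in either arm, judged at least possibly related to the injection or study procedures, pauses new injections pending review by the board and the IRB. The investigators and IRB should confirm the grade before enrolment begins.

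Optionally, add a clause that a halt does not cancel the adverse-event contacts already scheduled for women who have been injected.

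The cost is a sentence or two of protocol text and a possible short pause, with the probabilities tabulated in the working. Sample size, visit schedule and primary analysis do not change.
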